### 6.4.4.1 Reporting of serious adverse events that are also endpoints in the study

Since the study is to provide additional safety profile in Chinese population which is similar as the PLATO study population, the process of the reporting of serious adverse events that are also endpoints in the study is followed the process of PLATO study.

Suspected cardiac ischaemic events (including CV death, MI, stroke) should not be reported as AEs/SAEs. They are part of the natural history of the condition under investigation and therefore may be expected. Suspected cardiac ischaemic events will be analysed and presented.

Once an event has been identified, using their clinical judgement, investigators must determine if the event is an acute cardiac ischaemic event.

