### 6.3.3 Stroke

A stroke is defined as a neurological deficit caused by an ischaemic or haemorrhagic central nervous system event with residual symptoms at least 24 hours after onset or leading to death.

Stroke will be further sub-classified as:

• Ischaemic:

Ischemic stroke is defined as an infarction of the central nervous system tissue that results from a thrombus or embolus impairing central nervous system perfusion (and not primarily due to hemorrhage) with residual signs or symptoms lasting at least 24 hours after onset or leading to death. Hemorrhage may be a consequence of ischemic stroke. In this situation, the stroke should be recorded as an ischemic stroke with hemorrhagic transformation rather than a hemorrhagic stroke event.

• Haemorrhagic:

Hemorrhagic stroke is defined as an acute episode of focal or global cerebral or spinal dysfunction with a documented cause of intracranial hemorrhage on imaging (eg, computed tomography (CT) scan or magnetic resonance imaging (MRI) scan) either in the cerebral parenchyma, or in the subdural, epidural or subarachnoid space with residual signs or symptoms at least 24 hours after onset or leading to death. Evidence of hemorrhagic stroke obtained from lumbar puncture, neurosurgery, or autopsy can also confirm the diagnosis.

• Unknown/No imaging performed: if the type of stroke could not be determined by imaging or other means (from lumbar puncture, neurosurgery, or autopsy) but is judged to fulfill the stroke definition above, the stroke will be classified as ischaemic for purposes of the study.

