### **Disease progression**

Disease progression can be considered as a worsening of a subject's condition attributable to the disease for which the investigational product is being studied. It may be an increase in the severity of the disease under study and/or increases in the symptoms of the disease. The development of existing ischemia or death from vascular cause should be considered as disease progression and not an AE. Events, which are unequivocally due to disease progression, should not be reported as an AE during the study.

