### 6.4.4 **Reporting of serious adverse events**

All SAEs have to be reported, whether or not considered causally related to the investigational product, or to the study procedure(s). All SAEs will be recorded in the CRF.

If any SAE occurs in the course of the study, then investigators or other site personnel inform appropriate AstraZeneca representatives immediately, or **no later than 24 hours** of when he or she becomes aware of it.

The designated AstraZeneca representative works with the investigator to ensure that all the necessary information is provided to the AstraZeneca Patient Safety data entry site **on the day** of initial receipt for fatal and life threatening events **and within five calendar days** of initial receipt for all other SAEs.

For fatal or life-threatening adverse events where important or relevant information is missing, active follow-up is undertaken immediately. Investigators or other site personnel inform AstraZeneca representatives of any follow-up information on a previously reported SAE immediately, or **no later than 24 hours** of when he or she becomes aware of it.

Once the Investigators or other site personnel indicate an AE is serious in the WBDC system, an automated email alert is sent to the designated AstraZeneca representative.

If the WBDC system is not available, then the Investigator or other study site personnel reports a SAE to the appropriate AstraZeneca representative by telephone.

The AstraZeneca representative will advise the Investigator/study site personnel how to proceed.

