### 6.4.9 Other safety assessments

### 6.4.9.1 Bleeding events

For all bleeding events, the investigator will complete information on the CRF specific to that bleeding event. Additionally, bleeding events will be reported as AE and SAEs if serious criteria are met. Fatal/life-threatening and other major bleeding events are key components of primary endpoint (Wallentin 2009).

Fatal/life-threatening bleeding events are defined by 1 or more of the following criteria:

- Fatal
- Intracranial
- Intrapericardial bleed with cardiac tamponade
- Hypovolemic shock or severe hypotension due to bleeding and requiring pressors or surgery
- Clinically overt or apparent bleeding associated with a decrease in Hb of more than 50 g/L
- Transfusion of 4 or more units [whole blood or packed red blood cells (PRBCs) ] for bleeding.

Major other bleeding events are defined by 1 or more of the following criteria:

- Significantly disabling (eg, intraocular with permanent vision loss)
- Clinically overt or apparent bleeding associated with a decrease in Hb of 30 g/L to 50 g/L
- Transfusion of 2-3 units (whole blood or PRBCs) for bleeding.

Minor bleed is an event requiring medical intervention to stop or treat bleeding (eg, epistaxis requiring visit to medical facility for packing.

Minimal bleeds are events not requiring intervention or treatment (eg, bruising, bleeding gums, oozing from injection sites, etc).

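### Haemorrhagic stroke, fatal or not, carries opposite SAE reporting instructions in Protocol Sections 6.4.4.1 and 6.4.9.1, and no rule says which prevails

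*Protocol*

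**What the plan says.** - Section 6.4.4.1 exempts efficacy endpoints from safety reporting: "Suspected cardiac ischaemic events (including CV death, MI, stroke) should not be reported as AEs/SAEs". It gives as reasons that such events belong to the natural course of the disease and that the process follows PLATO. It adds that these events will be analysed and presented, and that the investigator decides whether an event is an acute cardiac ischaemic one.
- Section 6.3.3: "A stroke is defined as a neurological deficit caused by an ischaemic or haemorrhagic central nervous system event". The haemorrhagic subtype is spelled out: "Hemorrhagic stroke is defined as an acute episode of focal or global cerebral or spinal dysfunction with a documented cause of intracranial hemorrhage on imaging". It includes cases that lead to death.
- Section 6.4.9.1 requires a bleeding-specific CRF form for every bleed and then says: "Additionally, bleeding events will be reported as AE and SAEs if serious criteria are met". Under "Fatal/life-threatening bleeding events are defined by 1 or more of the following criteria", the first two criteria are fatal and intracranial.
- Section 6.4.3, under the heading on disease progression: "The development of existing ischemia or death from vascular cause should be considered as disease progression and not an AE".
- Section 6.3.1 leaves the split of deaths into cardiovascular and non-cardiovascular to the investigator.
- Section 6.4.4: "All SAEs have to be reported, whether or not considered causally related to the investigational product". Sites have at most 24 hours to inform the sponsor.

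**The concern.** A site that sees a haemorrhagic stroke finds two instructions. As a stroke, it is not to be reported as an AE or SAE. As an intracranial bleed, it must be. Nothing tells the site which to follow, and sites may differ.

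This matters because of the kind of study it is. Section 1.3 describes a post-approval study that the regulator required in order to describe safety, and bleeding is at the centre of its primary variables. Section 12.4 marks a data monitoring committee as not applicable, and events are judged locally (Section 3.2). Expedited SAE reporting is then the main route described for bringing a serious bleed to the sponsor's attention while the study runs, and the sponsor's right to stop the study on safety grounds (Section 9.5) depends on such information. A site that takes Section 6.4.4.1 at its word would send no 24-hour report for an intracranial bleed.

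**Working it through.** This is a question of text, so the sections are set side by side. No figure stated in the plan bears on it directly.

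1. **Non-fatal haemorrhagic stroke.** It is a stroke under 6.3.3, so 6.4.4.1 says not to report it. When shown on imaging it is an intracranial haemorrhage, so it meets the intracranial criterion of 6.4.9.1, which says to report it. The conflict is direct.
2. **Fatal haemorrhagic stroke.** It meets both the fatal and the intracranial criteria of 6.4.9.1. Under 6.4.4.1 it is exempt as a stroke, and possibly also as a cardiovascular death. The disease-progression text in 6.4.3 may exempt it again as a vascular death. The conflict is direct.
3. **Other fatal bleeds, for example gastrointestinal.** They meet the fatal criterion of 6.4.9.1. They come under 6.4.4.1 or the disease-progression text only if the investigator classes the death as cardiovascular or vascular. Section 6.3.1 gives no rule for fatal bleeds, so the conflict is possible but conditional.
4. **Precedence.** Neither section refers to the other. Section 6.4.4 states the general duty to report without mentioning the exemption. Amendment 1 changes exclusion criteria, ASA use, the dyspnoea text and the Hy's Law definition. It leaves this point alone.
5. **What is affected.** The primary variables in 11.2 are four PLATO-defined bleeding variables and the SAEs that are not bleeding. The bleeding form in 6.4.9.1 is required for all bleeds, whatever their AE status, so the bleeding counts do not depend on an SAE being filed. A haemorrhagic stroke or fatal bleed is outside the non-bleeding SAE variable under either instruction. What can be lost is the AE/SAE record and the prompt notice. The automatic alert in 6.4.4 is triggered when an AE is marked serious, and the protocol describes no such alert from the bleeding form.

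**Scale.** Inputs: 2000 planned patients (Section 3.1) and the ticagrelor rates of fatal bleeding in Table 1, which are 0.3% overall and 0.5% in China.

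- 2000 × 0.003 = 6
- 2000 × 0.005 = 10

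The China rate is one event in 207 patients (1/207 = 0.48%), so the upper figure is fragile. The range does not count the affected events. Fatal bleeds that are neither strokes nor classed as cardiovascular or vascular deaths fall out of it, and non-fatal haemorrhagic strokes come on top. The documents give no rate for the latter.

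**The case against.** The best defence is that 6.4.4.1 speaks of cardiac ischaemic events that belong to the natural course of the disease, and asks the investigator to confirm that the event is one. A haemorrhage is not ischaemic, and 6.4.9.1 deals with bleeding specifically. The disease-progression text likewise withholds AE reporting only for events unequivocally due to progression, which a gastrointestinal bleed on an antiplatelet drug would hardly be. Exempting efficacy endpoints is also a declared choice.

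Part of this stands. It makes the exemption of a non-stroke fatal bleed unlikely, which is why that part is conditional. It does not settle haemorrhagic stroke. The parenthesis names stroke without restriction, and no stroke is literally a cardiac event, so the label cannot show which strokes are meant.

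A reader might infer three stronger points that the documents do not support:

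- **That the primary bleeding rates are biased downwards.** The separate form for all bleeds protects them, provided the site recognises the event as a bleed.
- **That suspected but unconfirmed ischaemic events vanish from the primary SAE variable.** The protocol is silent on what follows a negative decision, and the general duty in 6.4.4 can be read to apply again. Suspected ischaemic events are also to be analysed and presented, and where they are tabulated may be left to an SAP that is not at hand. An explicit sentence would help, but this is a clarification.
- **That the default for strokes of undetermined type hides bleeds.** Under 6.3.3, "the stroke will be classified as ischaemic for purposes of the study" applies only when neither imaging nor other means settles the type. It is a sub-classification of stroke, and 6.4.9.1 classifies bleeding without reference to it.

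**Conclusion.** The contradiction between Sections 6.3.3, 6.4.4.1 and 6.4.9.1 is real for haemorrhagic stroke, fatal or not. For other fatal bleeds it depends on the investigator classing the death as cardiovascular or vascular.

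The consequence is inconsistent or missing AE/SAE and 24-hour reporting of some of the most serious bleeds. The documents do not support a claim of bias in a primary variable. The number of affected events cannot be computed from them; 6 to 10 fatal bleeds in 2000 patients gives only the order of magnitude, assuming the Table 1 rates carry over. The conclusion rests on the text and does not depend on that figure. The study is a safety commitment without a data monitoring committee, so the wording should be corrected.

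**What to change.** By amendment:

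1. In 6.4.4.1, limit the exemption to MI, ischaemic stroke and cardiovascular death not due to bleeding.
2. In the same place, state that haemorrhagic stroke, any other intracranial haemorrhage and any fatal bleed go on the bleeding form under 6.4.9.1 and are reported under 6.4.4, even when they also count as efficacy endpoints.
3. Bring the disease-progression text in 6.4.3 into line, so that a vascular death due to bleeding is not treated as progression, and add a cross-reference in 6.3.3.
4. As a secondary clarification, add one sentence to 6.4.4.1: a suspected event judged not to be an exempt endpoint is reported under 6.4.4 if it meets a seriousness criterion.

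The cost is a short amendment and a few more SAE reports. The endpoint definitions, the analysis and the sample size do not change.

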### 6.4.5 Laboratory safety assessment

Blood samples for determination of clinical chemistry, haematology, and urinalysis will be taken at the times indicated in the Study Plan and Time Schedule (see Table 2).

The following laboratory variables will be measured:

S-Creatinine S-Uric acid S-Alkaline phosphatase S-Aspartate aminotransferase (AST) S-Alanine aminotransferase (ALT) S-Total Bilirubin (Elevated values to be fractionated) S-Albumin B-Haemoglobin B-Haematocrit B-Platelets B-White blood cells

**NB.** In case a subject shows an AST or ALT  $\geq 3xULN$  and total bilirubin  $\geq 2xULN$  please refer to Appendix D 'Actions required in cases of combined increase of Aminotransferase and Total Bilirubin – Hy's Law', for further instructions.

For blood volume see Section 7.1.

## 6.4.6 Physical examination

A physical examination will be performed and include an assessment of the following: general appearance, respiratory, cardiovascular, abdomen.

# 6.4.7 ECG (Not applicable)

### 6.4.8 Vital signs

### 6.4.8.1 Pulse and blood pressure

Supine blood pressure and pulse rate will be measured using non-invasive equipment after 10 minutes rest on a bed. For timings of assessments refer to the Study Plan and Time Schedule (see Table 2)

### 6.4.9 Other safety assessments

### 6.4.9.1 Bleeding events

For all bleeding events, the investigator will complete information on the CRF specific to that bleeding event. Additionally, bleeding events will be reported as AE and SAEs if serious criteria are met. Fatal/life-threatening and other major bleeding events are key components of primary endpoint (Wallentin 2009).

Fatal/life-threatening bleeding events are defined by 1 or more of the following criteria:

- Fatal
- Intracranial
- Intrapericardial bleed with cardiac tamponade
- Hypovolemic shock or severe hypotension due to bleeding and requiring pressors or surgery
- Clinically overt or apparent bleeding associated with a decrease in Hb of more than 50 g/L
- Transfusion of 4 or more units [whole blood or packed red blood cells (PRBCs) ] for bleeding.

Major other bleeding events are defined by 1 or more of the following criteria:

- Significantly disabling (eg, intraocular with permanent vision loss)
- Clinically overt or apparent bleeding associated with a decrease in Hb of 30 g/L to 50 g/L
- Transfusion of 2-3 units (whole blood or PRBCs) for bleeding.

Minor bleed is an event requiring medical intervention to stop or treat bleeding (eg, epistaxis requiring visit to medical facility for packing.

Minimal bleeds are events not requiring intervention or treatment (eg, bruising, bleeding gums, oozing from injection sites, etc).

# 6.4.9.1.1 Bleeding associated with procedures

Bleeding associated with procedures should be reported as an AE/SAE if exceeding normal bleeding for the specific procedure.

### 6.4.9.1.2 Management of bleeding

There is currently no antidote to ticagrelor and treatment of bleeding should therefore be symptomatic and handled according to the clinical routines at the investigational centre.

- 6.5 **Patient reported outcomes (PRO) (Not applicable)**
- 6.6 **Pharmacokinetics (Not applicable)**
- 6.7 **Pharmacodynamics (Not applicable)**
- 6.8 **Pharmacogenetics (Not applicable)**
- 6.9 Health economics (Not applicable)

# 7. BIOLOGICAL SAMPLING PROCEDURES

# 7.1 Volume of blood

The total volume of blood that will be drawn from each subject in this study is as follows:

Assessment		Sample volume (mL)	No. of samples	Total volume (mL)
Safety	Clinical chemistry	5	3	15
	Haematology	2	3	6
Eligibility	Myocardial biomarker	5	1	5
Total				26

Table 3Volume of blood to be drawn from each subject

# 7.2 Handling, storage and destruction of biological samples

The samples will be used up or disposed of after analyses.

# 7.3 Labelling and shipment of biohazard samples

The Investigator ensures that samples are labelled and shipped in accordance with the Laboratory Manual.

# 7.4 Chain of custody of biological samples

A full chain of custody is maintained for all samples throughout their lifecycle.

The Investigator at each centre keeps full traceability of collected biological samples from the subjects while in storage at the centre until shipment or disposal (where appropriate) and keeps documentation of receipt of arrival.

The sample receiver keeps full traceability of the samples while in storage and during use until used or disposed of or until further shipment and keeps documentation of receipt of arrival.

AstraZeneca keeps oversight of the entire life cycle through internal procedures, monitoring of study sites and auditing of external laboratory providers.

# 7.5 Withdrawal of informed consent for donated biological samples

If a subject withdraws consent to the use of donated biological samples, the samples will be disposed of/destroyed, and the action documented. If samples are already analysed, AstraZeneca is not obliged to destroy the results of this research.

The Investigator:

- Ensures subjects' withdrawal of informed consent to the use of donated samples is notified immediately to AstraZeneca
- Ensures that biological samples from that subject, if stored at the study site, are immediately identified, disposed of /destroyed, and the action documented
- Ensures the laboratory(ies) holding the samples is/are informed about the withdrawn consent immediately and that samples are disposed/destroyed, the action documented and the signed document returned to the study site
- Ensures that the subject and AstraZeneca are informed about the sample disposal.

AstraZeneca ensures the central laboratory(ies) holding the samples is/are informed about the withdrawn consent immediately and that samples are disposed of/destroyed and the action documented and returned to the study site.

# 8. ETHICAL AND REGULATORY REQUIREMENTS

# 8.1 Ethical conduct of the study

The study will be performed in accordance with ethical principles that have their origin in the Declaration of Helsinki and are consistent with ICH/Good Clinical Practice, applicable regulatory requirements and the AstraZeneca policy on Bioethics and Human Biological Samples.

# 8.2 Subject data protection

The Informed Consent Form will incorporate (or, in some cases, be accompanied by a separate document incorporating) wording that complies with relevant data protection and privacy legislation.

# 8.3 Ethics and regulatory review

An Ethics Committee should approve the final study protocol, including the final version of the Informed Consent Form and any other written information and/or materials to be provided to the subjects. The investigator will ensure the distribution of these documents to the applicable Ethics Committee, and to the study site staff.

The opinion of the Ethics Committee should be given in writing. The investigator should submit the written approval to AstraZeneca before enrolment of any subject into the study.

The Ethics Committee should approve all advertising used to recruit subjects for the study.

AstraZeneca should approve any modifications to the Informed Consent Form that are needed to meet local requirements.

If required by local regulations, the protocol should be re-approved by the Ethics Committee annually.

Before enrolment of any subject into the study, the final study protocol, including the final version of the Informed Consent Form, is approved by the national regulatory authority or a notification to the national regulatory authority is done, according to local regulations.

AstraZeneca will handle the distribution of any of these documents to the national regulatory authorities.

AstraZeneca will provide Regulatory Authorities, Ethics Committees and Principal Investigators with safety updates/reports according to local requirements, including SUSARs (Suspected Unexpected Serious Adverse Reactions), where relevant.

# 8.4 Informed consent

The Investigator(s) at each centre will:

- Ensure each subject is given full and adequate oral and written information about the nature, purpose, possible risk and benefit of the study
- Ensure each subject is notified that they are free to discontinue from the study at any time
- Ensure that each subject is given the opportunity to ask questions and allowed time to consider the information provided
- Ensure each subject provides signed and dated informed consent before conducting any procedure specifically for the study
- Ensure the original, signed Informed Consent Form(s) is/are stored in the Investigator's Study File
- Ensure a copy of the signed Informed Consent Form is given to the subject
- Ensure that any incentives for subjects who participate in the study as well as any provisions for subjects harmed as a consequence of study participation are described in the informed consent form that is approved by an Ethics Committee.

# 8.5 Changes to the protocol and informed consent form

Study procedures will not be changed without the mutual agreement of the Principal Investigator and AstraZeneca.

If there are any substantial changes to the study protocol, then these changes will be documented in a study protocol amendment and where required in a new version of the study protocol (Revised Clinical Study Protocol).

The amendment is to be approved by the relevant Ethics Committee and if applicable, also the national regulatory authority approval, before implementation. Local requirements are to be followed for revised protocols.

AstraZeneca will distribute any subsequent amendments and new versions of the protocol to each Investigator(s). For distribution to Ethics Committee see Section 8.3.

If a protocol amendment requires a change to a centre's Informed Consent Form, AstraZeneca and the centre's Ethics Committee are to approve the revised Informed Consent Form before the revised form is used.

If local regulations require, any administrative change will be communicated to or approved by each Ethics Committee.

